4.8 Premature Termination or Suspension of Study

This study may be temporarily suspended or prematurely terminated if there is sufficient reasonable cause. If the study is prematurely terminated or suspended, the PI will promptly inform the IRB and will provide the reason(s) for the termination or suspension.

Circumstances that may warrant termination or suspension include, but are not limited to:

1. Determination of unexpected, significant, or unacceptable risk to participants
 - a. Clinical criteria that would meet such risks include, but are not limited to: permanent nerve damage, tissue necrosis, or wound healing complications that are directly related to the injection
2. Demonstration of efficacy that would warrant stopping
 - a. If patients receiving the injection require substantially less oral narcotic medication than those in the control group, such that continuing to withhold the medication was not in their best interest, the study may be discontinued.
3. Insufficient compliance to protocol requirements

CONFIDENTIAL

This material is the property of the NYU School of Medicine and Langone Medical Center. Do not disclose or use except as authorized in writing by the study sponsor

- 4. Data that are not sufficiently complete and/or evaluable
- 5. Determination of futility

5 Risks and Benefits

5.1 Potential Risks

There is no current standard of care in terms of trauma patients receiving these injections. At some institutions it is commonplace to give intra-operative injections for pain control. At NYU it is not standard practice for trauma surgery however this same cocktail of medications is given routinely during surgery to patients undergoing arthroplasty (i.e. total hip and total knee replacement). At this time based on NYU practice there is no risk of being in the control group and not receiving an injection. The risks of receiving an injection are related to the injection site and medication type.

Marcaine is characteristic of those associated with other amide-type local anesthetics. A major cause of adverse reactions to this group of drugs is excessive plasma levels, which may be due to overdosage, unintentional intravascular injection, or slow metabolic degradation. In this circumstance cardiac arrhythmia, respiratory distress, restlessness, anxiety, and seizure may occur. These risks, however, are minimal as the dosage given in this study is the lowest effective dose and the technique of administration minimizes such an outcome.

Ketorolac is an NSAID and carries a risk of GI distress and renal damage. NSAID use will be diminished in patients with poor renal function as described. Post-operative labs are ordered as the standard of care and will allow physicians on the treatment team to identify any renal compromise.

Morphine sulfate (duramorph) is a narcotic medication which carries a risk of constipation, respiratory distress, sedation, and dependence if given in excess or if given over a prolonged period of time. In this study duramorph will be given once, limiting the likelihood of any complication.

Patients are also monitored constantly during surgery by anesthesia and afterwards by physicians and nurses to identify complications. These medications are given during surgery using the lowest effective dose for the shortest duration consistent with patient treatment goals in order to minimize risk.

An injection of these medications given into a blood vessel can cause unintended systemic effects as described above and an injection given into a nerve can cause temporary numbness or weakness. Injections will be performed by trained surgeon under direct visualization to prevent nerve damage and withdraw-inject method will be used to prevent intravascular injection.

All oral and IV medications given after surgery are standard of care and pose no new risk to patients as they would already be receiving them. The only change in this study is adhering to this regimen whereas in practice some medications might get missed.

The potential risks to the research subjects also include possible a loss of confidentiality of sensitive information collected for this study. The risk of loss of confidentiality of the data is negligible under rigorous application of appropriate procedures for data security.

CONFIDENTIAL

This material is the property of the NYU School of Medicine and Langone Medical Center. Do not disclose or use except as authorized in writing by the study sponsor

Interventional Template Version: 28 APR 2017

5.2 Potential Benefits

Some subjects may experience better pain control, improved satisfaction, decreased need for narcotics and decreased side effects. If the study is not inconclusive, the study's results may benefit future patients by helping to confirm the benefits of multimodal regimens in the setting of orthopaedic trauma patients, furthering the case for them to become the standard of care for peri- and postoperative pain control.

6 Statistical Analysis

6.1 General Approach

As treated Sample. The primary analyses will follow the as-treated principle in order to evaluate the true outcome of the intervention as experienced by the patient who is blinded to the intervention.

Missing Data. It is anticipated that the data for some subjects will be incomplete for various reasons: missed clinic visits, refusal to answer a sensitive question on a questionnaire, onset of illness, loss-to-follow-up, etc. All occurrences of incomplete data will be investigated to carefully document the reasons for the missing data.

Sensitivity Analyses. To evaluate the robustness of the main results to reasonable perturbations of the methods and assumptions used, competing statistical methods (those not used in the main analyses) will be relegated to serving as a guide to our confidence in the main results.

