Statistical Analysis	As treated analysis will be performed with mean, t-tests, within and between group ANOVA, linear regression, Mann- Whitney-Wilcoxon tests

CONFIDENTIAL

This material is the property of the NYU School of Medicine and Langone Medical Center. Do not disclose or use except as authorized in writing by the study sponsor
Interventional Template Version: 28 APR 2017

1 Key Roles

PI: [name]
Department of Orthopedic Surgery and Cell Biology
NYU Langone Medical Center
[name]
[contact]
[contact]

Co-PI:

[name]
Assistant Professor of Anesthesiology
NYU Langone Orthopedic Hospital
NYU Langone Health
[name]
[name]
[contact]

2 Background and Specific Aims

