3.1 Description of Study Design

The researchers will use NYU admission records, emergency room records, orthopedic consult records, and immediate care records to identify patients eligible for participation in the study. Orthopedic residents and authorized researchers will consent and enroll patients pre-operatively.

Subjects with a qualifying fracture will be randomized to either the SSI or control group. Subjects in the SSI group will receive a peri-incisional injection of 40cc 0.25% bupivacaine (marcaine), 5 mg morphine sulfate (duramorph) (1 mg/cc, 5 cc total), and 30 mg of ketorolac (30 mg/cc, 1 cc total) into soft-tissue and musculature surrounding the fracture site and 0.25% Bupivacaine (Marcaine) 10 mL into the subcutaneous tissue surrounding the surgical incision. The control group will receive no injection. The injection will be administered by the subjects NYU orthopedic surgeon, all of whom are familiar with the technique. The patient will be blinded to if a medication is being injected. Subjects will not receive ketorolac if they have kidney disease or a history of allergy to NSAIDS or aspirin. The dose of ketorolac will be reduced to 15 mg (30 mg/cc, 0.5cc total) in subjects older than 65 years of age, in subjects with a history of peptic ulcer disease, a CrCl of 30 to 50 ml/min, or subjects with diabetes. These modifications are recommended by the manufacturer and are used in standard practice. A sub group analysis will be done on patients who receive this lower dosage to see if it has an impact on the data.

After initial recruitment, subjects' pain will be assessed via visual analog scale (VAS) by nursing staff on a q4h basis. A standardized regimen of pain medication will be given to all subjects who are enrolled. Pre-operatively subjects will receive acetaminophen 1gm oral (every 6-8 hours, not to exceed 4gm daily) and meloxicam 15mg oral once daily. Post-operatively, subjects will receive acetaminophen 1gm oral (every 6-8 hours, not to exceed 4gm daily), ketorolac 30mg injection, once daily in AM, starting POD 1(15mg for patients >65 years of age and/or renal impairment), and pregabalin (Lyrica) 50mg oral every 8 hours (held for sedation). Ice PRN for mild pain, tramadol 50mg oral every 8 hours PRN for moderate pain, and tramadol 100mg oral every 8 hours PRN for severe pain. Oxycodone 5mg oral every 6 hours PRN will be given for breakthrough pain.

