4.2 Exclusion Criteria

An individual who meets any of the following criteria will be excluded from participation in this study:

1. Pregnant women
2. Treatment with Arthroplasty
3. Patients who receive a peripheral nerve block
4. Patients who receive intra-op or post-op ketamine
5. Patients with concomitant TBI or MR
6. Polytrauma patients
7. Pathologic Fractures
8. Patients with a contraindication to any of the medications on the study list due to other medical problems such as renal or liver disease or due to allergy/intolerance
9. Patients with prior extremity weakness resulting from stroke or other neurological condition
10. Prior or current history of narcotic use
11. Patients with advanced dementia
12. NYUMC Students, Residents, Faculty

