6.2 Analysis of Endpoints

Primary Endpoints:

amount (mg) of narcotics (oral morphine mg equivalents) used
duration of narcotic use
patient reported pain scores

Secondary Endpoints:

length of stay
progress with physical therapy: distance ambulated, range of motion, exercises done
reported long-term narcotic use at home/SAR
discharge location: home, acute rehab, skilled nursing facility
documented narcotic refills
falls
adverse events

The analysis of narcotic Use, VAS, APS-POQ, and SMFA scores will rely on a univariate repeated-measures analysis of variance model for mean score. This model is in the class of models commonly known as a unirep-ANOVA models. It assumes that the mean score is a function of elapsed time and the treatment regimen assigned. This model takes into account the fact that the subject's repeated measures are correlated. The fitted model will provide statistical estimates of the mean levels, the treatment-effect differences between mean levels, the standard deviation, the intra-class correlation coefficient, 95% CIs, standard errors (SE), and statistical hypothesis tests. The estimates of means will be used to compute summary criteria such as area under the curve (AUC) for each regimen. All estimates reported will be presented their 95% CIs.

CONFIDENTIAL

This material is the property of the NYU School of Medicine and Langone Medical Center. Do not disclose or use except as authorized in writing by the study sponsor

Interventional Template Version: 28 APR 2017

All endpoints will be evaluated as fits the data set with graphical figures such as scatter plots, box-and-whisker plots, and frequency histograms to visualize the distribution of these outcomes and their relationships to covariates and treatment assignment. When appropriate descriptive graphical and tabular methods, and Kaplan-Meier curves will also be estimated and presented in a graphical figure.

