6.4 Enrollment/Randomization/Masking Procedures

As per standard of care, an anesthesiologist will determine if subjects receive general or spinal anesthesia. Within these groups subjects will randomized to receive a SSI or no intervention. Randomization will be done via redcapautomated computer randomization. After randomization the surgical team will be informed which group the patient has been randomized into.

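### The primary analysis is as-treated with no assigned-arm analysis named, and no rule covers patients who meet an exclusion criterion after randomisation

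*Combined protocol and SAP*

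**What the plan says.** **Analysis principle.** Section 6.1: "The primary analyses will follow the as-treated principle in order to evaluate the true outcome of the intervention". The Protocol Summary agrees: "As treated analysis will be performed with mean, t-tests". The sensitivity paragraph in 6.1 refers only to unspecified alternative methods and names no other analysis set. Section 6.2 describes the repeated-measures model differently: "It assumes that the mean score is a function of elapsed time and the treatment regimen assigned".

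**Who controls delivery.** Section 6.4: "After randomization the surgical team will be informed which group the patient has been randomized into". Section 3.1: "The injection will be administered by the subjects NYU orthopedic surgeon". The reason given in 6.1 for as-treated is that the patient is blinded.

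**Exclusions.** Section 4.2 opens: "An individual who meets any of the following criteria will be excluded from participation in this study". Its list includes "Patients who receive intra-op or post-op ketamine" and, without a time limit, a peripheral nerve block. Section 4.7 gives the investigator discretion to end participation when an exclusion criterion is newly met and rules out continuing. Section 4.6 expects 300 to 350 evaluable patients out of 400 and does not define evaluable; section 6.3 suggests that the allowance is mainly for loss to follow-up.

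**The concern.** Randomisation makes the assigned arms comparable. Grouping patients by what they received keeps that comparability only if departures from assignment are unrelated to outcome. Here the people who decide whether the injection is given know the allocation, so a patient might go uninjected for reasons linked to later pain or narcotic use. The as-treated estimate would then mix the effect of the injection with those reasons, and the bias could go either way. Sections 6.1 and 6.2 would also give different primary results, with nothing to say which governs.

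The exclusion list raises a second route to bias. Section 3.1 says "Orthopedic residents and authorized researchers will consent and enroll patients pre-operatively", and the injection is given during surgery, so post-operative ketamine always comes after randomisation. It may depend on pain, which is a primary outcome. If these patients are removed and there are more of them among controls, a real benefit is understated. The same question arises for intra-operative ketamine or a nerve block if given after randomisation; the documents do not fix that timing.

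**Working it through.** **Inputs from the documents.** SD 25 mg and difference 15 mg/day (6.3); 10 mg/day (Summary endpoint); 100 per arm in each anaesthesia cohort (section 3), hence 200 per arm if the cohorts are pooled. Pooling is an assumption, since no pooled primary test is specified. Crossover and ketamine rates are not given; all those below are assumed.

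**The plan's own figure.** For 15 mg, SD 25 mg, two-sided 0.05 and power 0.80, a t-test needs 44.6, so 45 per arm. The 90 in 6.3 reproduces as 2 × 45 if its group means one anaesthesia group with both arms. The point here does not depend on that figure.

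**1. As-treated bias when there is no true effect.** Let p be the share of injection-assigned patients not injected, and s their excess use over those injected. Only this direction is modelled, because 5.1 says the injection is not routine in trauma surgery at this institution. With overall mean μ:

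- injected mean = μ − ps
- as-treated control mean = μ + p(1 − p)s/(1 + p)
- spurious difference = 2ps/(1 + p)
- SE = 25 × √[1/(n(1 − p)) + 1/(n(1 + p))]

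Mid case, p = 0.05 and s = 10: 2 × 0.05 × 10/1.05 = 0.95 mg/day. At n = 100 the SE is 25 × √(1/95 + 1/105) = 3.54, giving a shift of 0.27 SE.

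| p | s (mg/day) | Bias (mg/day) | Type I error, 100 per arm | Type I error, 200 per arm |
|---|---|---|---|---|
| 0.02 | 5 | 0.20 | 0.0504 | 0.0507 |
| 0.05 | 5 | 0.48 | 0.0521 | 0.0542 |
| 0.05 | 10 | 0.95 | 0.0583 | 0.0667 |
| 0.10 | 10 | 1.82 | 0.0805 | 0.1118 |
| 0.10 | 15 | 2.73 | 0.1197 | 0.1921 |

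Simulating the mid case (20,000 trials) gave 0.060 and 0.067 as-treated, against 0.052 and 0.048 by assigned arm. This is a single-outcome test with complete data, used to illustrate the model in 6.2. The sign reverses if uninjected patients use less.

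**2. Removing post-operative ketamine patients, true difference 10 mg.** Suppose the top share q of controls on latent pain is removed at cut-off k, with the same cut-off in the injection arm, where latent pain is lower by d SD (0.40 = 10/25, or 0.24 = 0.6 × 0.40). With correlation ρ between pain and use, the fall in an arm's mean is 25ρφ(k)/(1 − q). For injected patients, k + d and their own removal rate are used. For example, with 2% of controls and ρ = 1: 10 − 1.235 + 0.495 = 9.26.

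If the patients are kept instead, and ketamine spares 5 to 25 mg/day of narcotic, the difference shrinks by (control rate − injection rate) × sparing.

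| Controls | Injection arm | ρ | d | Estimate if removed | Loss if removed (mg) | Loss if kept (mg) |
|---|---|---|---|---|---|---|
| 2% | 0.71% | 1.0 | 0.40 | 9.26 | 0.74 | 0.06–0.32 |
| 2% | 0.71% | 0.6 | 0.40 | 9.56 | 0.44 | 0.06–0.32 |
| 2% | 1.09% | 0.6 | 0.24 | 9.69 | 0.31 | 0.05–0.23 |
| 5% | 2.04% | 1.0 | 0.40 | 8.54 | 1.46 | 0.15–0.74 |
| 5% | 2.04% | 0.6 | 0.40 | 9.13 | 0.87 | 0.15–0.74 |
| 5% | 2.97% | 0.6 | 0.24 | 9.42 | 0.58 | 0.10–0.51 |

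In every row keeping the patients distorts less than removing them, provided sparing is no more than 25 mg/day.

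**The case against.** The strongest reply is that this may never matter. The intervention is one injection given in theatre by a surgeon who has been told the allocation, with no adherence period. Nothing in the documents predicts crossover, and with none the two analyses are identical. Even the mid case moves type I error only from 0.05 to 0.058. That is right, and the top of the range should not set the weight of the point. But if crossover is rare, assigned-arm analysis costs almost nothing, so rarity is no argument for as-treated.

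A second reply is that 4.2 and 4.7 can be read together: 4.2 sets eligibility, and 4.7 handles criteria that appear later. This softens the conflict between mandatory and discretionary wording. It does not supply an analysis rule, which is the more important gap. Likewise, the wording in 6.2 may be generic, but the plan still does not say which classification governs.

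Third, ketamine is not part of the standard regimen, so use may be rare, and removal biases towards no effect. Keeping these patients also distorts. At 50 mg/day of sparing, the loss from keeping them at the 2% rate would be (0.02 − 0.0071) × 50 = 0.65 mg in the first two rows, so keeping would be worse in two of the three 2% scenarios. The preference for keeping them on these numbers therefore depends on moderate sparing. The case for a rule fixed in advance does not.

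**Conclusion.** The concern holds. A stated primary rule gives a biased answer whenever delivery departs from allocation for reasons linked to outcome, and it conflicts with the model in 6.2. Patient blinding is no safeguard when the surgical team knows the assignment.

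The size is unknown. It is zero with no crossover; the mid case of 0.95 mg/day is 10% of the Summary's 10 mg and 6% of the 15 mg in 6.3. The 200-per-arm results also assume pooled cohorts. The ketamine issue is smaller, a loss of 0.31 to 1.46 mg from a true 10 mg over the assumed rates, and on its own calls mainly for a stated rule. Assigned-arm analysis without such removals takes away both biases, but not bias from missing data.

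**What to change.** - **Section 6.1 and Summary:** make the primary analysis all randomised patients by assigned arm, consistent with 6.2. Keep as-treated as a supportive analysis, with treated defined in advance, including patients whose ketorolac component was reduced or omitted under 3.1.
- **Sections 4.2 and 4.7:** reconcile them so that criteria met only after randomisation do not remove patients from follow-up or from the primary analysis set. This concerns follow-up and analysis only, not whether those treatments are given.
- **Ketamine:** report use by arm and add one sensitivity analysis, because ketamine is absent from the conversion tables in 14.1. Medications are already recorded under 6.2.1.
- **Section 4.6:** define evaluable to match.

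The cost is wording in five places, one table and one sensitivity analysis. There is slight dilution if patients cross over: with 5% uninjected at random, a true 10 mg effect is estimated as 10 × 0.95 = 9.5 mg. On the 15 mg in 6.3, power stays at 0.98 with 5% crossover and 100 per arm (effect 14.25 mg), and at 0.84 with 20% crossover and 75 per arm (effect 12 mg). The change to 4.2 and 4.7 is needed while patients are being followed, because follow-up that has been stopped cannot be recovered at analysis.

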6.3 Sample Size

In order to have a sufficient N to power the study a minimum of 200 subjects per anesthesia group will be recruited ($\alpha=0.05$, $\beta=0.2$). If the difference in the morphine equivalent consumption, is found to be 15mg daily with a standard deviation between the groups of 25mg, we will need 90 subjects per group in order to reject the null hypothesis with the probability (power) 0.8. The Type I error probability associated with this test of this null hypothesis is 0.05. To allow for within group analyses and accommodate for the poor follow-up rate in fracture patients we will need 400 patients.

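### No analysis rule for missing data: the named repeated-measures ANOVA leaves partial records undecided, and duration of narcotic use has no censoring rule

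*Combined protocol and SAP*

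**What the plan says.** Section 6.1 (General Approach) expects gaps: "It is anticipated that the data for some subjects will be incomplete for various reasons", among them missed visits and loss to follow-up. The response is that "All occurrences of incomplete data will be investigated to carefully document the reasons for the missing data". It gives no imputation method, missingness assumption or rule for partial records. The sensitivity paragraph says that "competing statistical methods (those not used in the main analyses) will be relegated to serving as a guide to our confidence in the main results"; it names no method and is not tied to missing data.

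Section 6.2 (Analysis of Endpoints) says that the analysis of narcotic use, VAS, APS-POQ and SMFA "will rely on a univariate repeated-measures analysis of variance model for mean score", and adds: "This model is in the class of models commonly known as a unirep-ANOVA models". The promised output includes "the standard deviation, the intra-class correlation coefficient, 95% CIs, standard errors (SE), and statistical hypothesis tests". The section does not say how the model is fitted.

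Section 6.2 also makes duration of narcotic use a primary endpoint. The test list in the Protocol Summary is general: t-tests, ANOVA, linear regression and Mann-Whitney-Wilcoxon. For censored data, section 6.2 says only that, when appropriate, "Kaplan-Meier curves will also be estimated" and shown in a figure.

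Section 6.3 sets 400 patients partly to "accommodate for the poor follow-up rate in fracture patients". Section 4.6 expects 300 to 350 evaluable patients of 400 and does not define evaluable.

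**The concern.** A larger enrolment protects power. It does not say how a patient with some readings missing enters the analysis, and it does not remove bias.

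Three things are at stake:

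- **Who is analysed.** Classical univariate repeated-measures ANOVA needs a common, complete set of times, so one missed call removes the patient. The same mean model fitted by likelihood with a random patient effect keeps partial records. The plan does not choose between the two.
- **Correlation.** A single intra-class correlation fits an equal-correlation assumption. The measurements run from four-hourly inpatient VAS to monthly calls (section 3.1), where equal correlation is implausible.
- **Bias.** Patients in more pain, or those who go home sooner, may have more gaps. Section 2.3 hypothesises that the injection shortens the stay, so the amount of inpatient data may itself differ by arm.

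For duration, a patient lost while still taking an opioid has an unknown stop time. Dropping such patients, or counting them as stopped, would tend to shorten the estimate, more so in an arm with more loss. The documents give no reason to say which arm that would be.

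**Working it through.** **1. The plan's own sample size.** Section 6.3 uses a 15 mg daily difference, SD 25 mg, alpha 0.05 (taken as two-sided) and power 0.8. Per arm, n = 2 × (1.960 + 0.842)² × (25/15)² = 43.6, so 44; the t-test version gives 44.6, so 45. Two arms make 90. The stated 90 is reproduced if a group there means an anaesthesia group, but not if it means a treatment arm.

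**2. Number of calls (section 3.1; three months' participation in the Protocol Summary).** Week 1 has at most 3 to 4, week 2 has 2, weeks 3 and 4 have 1 each, and the later monthly calls add 1 to 2. The total is 8 to 10. Aim 2 (section 2.2) measures narcotic use for two weeks after surgery, which covers at most 5 to 6 calls.

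**3. Complete cases, independent misses.** With a miss rate m per call and k calls, the expected complete number is 400 × (1 − m)^k. The documents do not give m; 2% to 20% is an assumed range.

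| m | k = 5 | k = 6 | k = 8 | k = 10 |
|---|---|---|---|---|
| 2% | 362 | 354 | 340 | 327 |
| 5% | 310 | 294 | 265 | 239 |
| 10% | 236 | 213 | 172 | 139 |
| 20% | 131 | 105 | 67 | 43 |

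Keeping 300 complete requires m ≤ 1 − (300/400)^(1/k), which is 2.8% for 10 calls and 3.5% for 8. Keeping 350 requires 1.3% and 1.7%.

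**4. Complete cases, clustered misses.** Loss to follow-up clusters within patients. Under a beta-binomial with within-patient correlation ρ, let s = 1/ρ − 1, a = (1 − m)s and b = ms. The complete share over 10 calls is B(a + 10, b)/B(a, b). For ρ = 0.2, 0.4 and 0.6, 10% missed leaves 229, 278 and 312 of 400; 5% missed leaves 304, 334 and 354.

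**5. Power in the independent 10%, 10-call case.** About 34.9 patients per arm remain in each anaesthesia cohort, or 69.8 per arm pooled. As a rough guide, power for a single mean difference is Φ(δ/(25√(2/n)) − 1.96).

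- 15 mg: 71% within a cohort, 94% pooled.
- 10 mg (the endpoint threshold in the Protocol Summary): 39% within a cohort, 66% pooled.

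**6. The same mean model fitted by likelihood.** With a random intercept, a patient with j of 10 calls contributes information j/(1 + (j − 1)ICC) on the mean. Averaging over binomial j and dividing by the full-data value, for ICC 0.3 to 0.7, retains 97.7% to 99.5% at 10% missed and 95.0% to 98.8% at 20%. Complete cases retain 35% and 11% of patients.

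**7. Which outcomes the call count fits.** Outpatient pain fits it best. APS-POQ is collected twice (first post-operative day, and four to eight weeks after injury). SMFA is collected once, so a repeated-measures model does not apply to it.

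**The case against.** The strongest reply is that nothing in the plan says incomplete patients are excluded. Section 6.2 names no fitting method, and its promised output, including the intra-class correlation, could come from a random-intercept mixed model that keeps partial records. This stands. A reader might infer that the trial will lose well over a third of its patients, but that needs listwise deletion, an assumed miss rate, independent misses, and every call serving as a model time point. None of the four is stated. Week 1 calls are only an upper limit, and clustering or the two-week window shrinks the loss.

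It is also tempting to set the complete-case counts against the 300 to 350 evaluable patients as a contradiction. Evaluable is undefined, so the two may count different things.

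A reader might further infer that the trial becomes underpowered. For the pooled 15 mg difference it does not: power is still about 94% in the independent 10% case.

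On duration, it is tempting to say that a patient lost on opioids will be counted as stopped, or that duration will be tested by a t-test. No section assigns a test to duration or states such a rule. Refill checks in Epic and pharmacy records (section 3.1) give some information independent of the calls, though a refill record does not show when tablets were last taken.

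What the reply does not remove is the ambiguity. In the independent 10% case over 10 calls, one named model could analyse about 139 patients, or all who have at least some data, depending on a fitting choice left open. The equal-correlation assumption remains under a random-intercept fit.

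**Conclusion.** The concern holds in conditional form. The plan expects missing data and poor follow-up but gives no method for analysing them. It names a model that classically needs complete records and assumes equal correlation, and it gives no censoring rule or time-to-event test for a primary endpoint.

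The patient loss is an illustration, not a forecast: in the complete-case 8-to-10-call scenarios at 5% to 10% missed, about 139 to 265 of 400 remain if misses are independent, and more remain if they cluster or if only the two-week window counts. The main risk is selection bias from gaps related to pain, opioid use or early discharge. Power becomes a concern for within-cohort comparisons and for a 10 mg difference. These choices should be fixed before outcome data are seen.

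**What to change.** In section 6.2, replace the univariate ANOVA for repeatedly measured outcomes with a likelihood-based mixed model for repeated measures that uses all observed values. Include treatment, time, treatment-by-time and anaesthesia stratum, with baseline VAS for pain, and a covariance not restricted to equal correlation. List the time points for each outcome, and take SMFA out of this model.

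In section 6.1, state the missing-at-random assumption and add one delta-adjusted missing-not-at-random sensitivity analysis. In section 4.6, define evaluable.

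Analyse duration as time to last reported opioid use, censored at last contact, with a log-rank test stratified by anaesthesia type. Say that stop dates learned from weekly or monthly calls are known only to an interval, and fix the dating convention in advance.

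The cost is SAP wording, standard software, slightly more analysis work and more covariance parameters to estimate. Section 3.1 has the calls record reported usage but does not mention a last-use date; if the call form lacks one, it needs one added question.
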